14.0 DETERMINATION OF SAMPLE SIZE

The primary efficacy parameter is the change from baseline to Week 8 during the double-blind treatment period in CDRS-R total score. A sample size of 400 patients (160 per group for placebo and vilazodone, and 80 for fluoxetine) was initially planned to provide 85% power to detect an effect size of 0.36 (treatment group difference of 4 units relative to pooled standard deviation of 11.1) for the primary efficacy parameter, based on an MMRM model using simulation method (Lu, 2012). The simulation assumed a correlation of 0.7 between the repeated measures, and a dropout rate of 17%, based on historical studies in pediatric patients with MDD.

Based on the planned blinded interim analysis which included the first 300 randomized patients (75% of the initial sample size), the study sample size was increased to a total of 455 patients (182 per group for placebo and vilazodone, and 91 fluoxetine patients) based on a pooled standard deviation of 12.3. During the teleconference with the FDA on the increased sample size, the FDA recommended a second interim analysis to be performed when the study enrolled the initially planned sample size of 400 patients. The second interim analysis included 427 randomized patients and the pooled standard deviation was 12.43. Therefore, a sample size of 470 patients (188 per group for placebo and vilazodone, and 94 for fluoxetine) is required to maintain the 85% statistical power to detect a treatment difference of 4 units for the primary efficacy endpoint.

[figure not shown]
15.0 STATISTICAL SOFTWARE

Statistical analyses will be performed using version [REDACTED]
[REDACTED]

16.0 DATA HANDLING CONVENTIONS

16.1 VISIT TIME WINDOWS

[Table 16.1–1](#) and [Table 16.1–2](#) present the visits assigned for efficacy and safety analyses and the corresponding ranges of treatment days (window) during which an actual visit may occur.

16.2 DERIVED EFFICACY VARIABLES

The efficacy variables are derived as follows:

- *CDRS-R responders* are defined as patients with a $\geq 40\%$ reduction from baseline in CDRS-R total score. The value is 1 for CDRS-R responders and 0 otherwise
- *CDRS-R remitters* are defined as patients with $CDRS-R \leq 28$. The value is 1 for CDRS-R remitters and 0 otherwise

The total score at a particular visit will be calculated using $(\text{sum of nonmissing items}) \times (\text{total number of items}) / (\text{number of nonmissing items})$ only if the number of missing items is ≤ 2 for the CDRS-R score.

If a patient misses a postbaseline visit or if his/her postbaseline visit is outside of the visit time window, a record for the scheduled visit will be imputed using the last observed nonmissing value immediately before the missing value. If the missing value occurs at Week 1, the baseline value will be carried forward for Week 1, provided that at least 1 subsequent postbaseline assessment is available. For a composite scale such as CDRS-R total score, individual items of the rating scale will not be carried forward. Only total scores will be carried forward using the LOCF approach.

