#### **9.3.1 Inclusion Criteria**

To be eligible to participate in the study, patients must meet the following criteria:

1. Be able to provide informed assent and their parent/guardian/LAR and caregiver must provide written informed consent before the initiation of any study-specific procedures (Section 5.3)
2. Be a male or female outpatient, 7 to 17 years of age, inclusive, at Screening (Visit 1)
3. Meet DSM-IV-TR criteria for MDD, confirmed by K-SADS-PL, with a current depressive episode of  $\geq$  6 weeks duration at Screening (Visit 1)
4. Have a score of  $\geq$  40 on the CDRS-R at Screening (Visit 1) and Baseline (Visit 2)
5. Have a Clinical Global Impressions-Severity (CGI-S) score  $\geq$  4 at Screening (Visit 1) and Baseline (Visit 2)

6. Have a caregiver who is willing and able to be responsible for safety monitoring of the patient, provide information about the patient's condition, oversee the administration of investigational product, and accompany the patient to all study visits (Section 5.3)
7. Have normal physical examination findings, vital sign values, clinical laboratory test results, and electrocardiograms (ECG) results, or abnormal results that are determined by the Investigator not to be clinically significant
8. Must have a negative serum pregnancy test result if patient is female  $\geq$  9 years of age or has had onset of menses.

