#### **9.5.1.2.1               Primary Efficacy Assessment: Children's Depression Rating Scale-Revised**

The CDRS-R ([Poznanski and Mokros, 1996](#)) is a semi-structured, clinician-rated instrument designed for use with children and adolescents between the ages of 6 to 17 years. It contains 17 ordinally-scaled items that evaluate the presence and severity of symptoms commonly associated with depression in childhood. The CDRS-R score ranges from 17 to 113.

The CDRS-R will be administered separately to the patient and to the caregiver. For each item, the rating that provides the best description of the patient will be selected by the clinician administering the interviews.

A copy of the CDRS-R is provided in [Appendix V](#).

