10.1 PRIMARY EFFICACY PARAMETER

The primary efficacy parameter is the change from baseline to Week 8 in CDRS-R total score. The primary analysis for comparing vilazodone vs placebo will be performed using an MMRM with treatment group, pooled study center, visit, and treatment-group-by-visit interaction as the fixed effects and the baseline value and baseline-value-by-visit interaction as the covariates. An unstructured covariance matrix will be used to model the covariance of within-patient scores. The Kenward-Roger approximation (Kenward and Roger, 1997) will be used to estimate denominator degrees of freedom. This analysis will only use the observed cases of postbaseline scores without imputation of missing values.

To control the overall type I error rate for the multiple comparisons across the primary and the secondary hypotheses, a fixed sequence procedure will be applied. Details are provided in Section [10.2](#).

In addition, two sensitivity analyses, LOCF and pattern-mixture model approaches, will be performed on the primary efficacy parameter. The LOCF approach is based on an analysis-of-covariance (ANCOVA) model including treatment group and pooled study center as factors and baseline CDRS-R total score as a covariate. Another sensitivity analysis using a pattern-mixture model approach based on non-future dependent missing value restrictions (Kenward et al., 2003) will be performed to assess the robustness of the primary MMRM results to the possible violation of the missing-at-random assumption. The details of this sensitivity analysis are as follows:

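### Does a 40% cut in the raw CDRS-R total, on a scale that starts at 17, make the responder variable unsound because some remitters are coded as non-responders?

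*SAP*

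**What the plan says.** SAP 16.2 (Derived Efficacy Variables) defines two binary variables from the CDRS-R total. Response requires a relative fall of at least 40%: "reduction from baseline in CDRS-R total score. The value is 1 for CDRS-R responders and 0 otherwise". Remission is an absolute level, a total of 28 or less: "The value is 1 for CDRS-R remitters and 0 otherwise".

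Protocol 9.5.1.2.1 describes the instrument: "It contains 17 ordinally-scaled items", and "The CDRS-R score ranges from 17 to 113". Protocol 9.3.1 (criterion 4) sets the entry threshold at 40, at both Screening and Baseline.

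Neither variable is the primary or key secondary parameter. SAP 10.1 states: "The primary efficacy parameter is the change from baseline to Week 8 in CDRS-R total score". SAP 10.2 names the change in CGI-S score as the secondary parameter. No visible text subtracts the scale minimum, states that a remitter counts as a responder, or shows how either binary variable will be analysed.

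**The concern.** Seventeen points of every total can never be lost, so a percentage taken on the raw total understates improvement relative to what is attainable, and most of all for the mildest patients. At the entry score of 40, a raw 40% fall uses up 70% of the attainable range; at 80 it uses 51%. Near the entry threshold the response cut-off drops below the remission cut-off, and the outcome usually read as the lesser one becomes the harder to reach.

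What would be at stake is interpretation. A responder table could count as non-responders some children who meet the plan's own remission criterion, and the word response would mean something different by baseline severity.

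**Working it through.** **Inputs.** Response rule, at least 40% of the raw total, and remission rule, 28 or less (SAP 16.2). Scale 17 to 113 (protocol 9.5.1.2.1). Lowest eligible baseline 40 (protocol 9.3.1). SD of change 12.43 and total of 470 patients, 188 per main arm (SAP 14.0). The plan states no figure on this point, so there is none to reproduce.

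**Step 1: where the rules cross.** With baseline b and visit score y, response means y ≤ 0.6b. A remitter (y ≤ 28) can fail this only if 0.6b < 28, that is b < 28/0.6 = 46.67.

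| Baseline | Response cut-off 0.6b | Remitter scores coded non-responder |
|---|---|---|
| 40 | 24.0 | 25–28 |
| 41 | 24.6 | 25–28 |
| 42 | 25.2 | 26–28 |
| 43 | 25.8 | 26–28 |
| 44 | 26.4 | 27–28 |
| 45 | 27.0 | 28 |
| 46 | 27.6 | 28 (18/46 = 39.1%) |
| 47 | 28.2 | none (19/47 = 40.4%) |

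SAP 16.2 allows prorated totals with up to 2 missing items. The highest prorated baseline that can be discordant is 41 × 17/15 = 46.47, so the range does not widen.

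**Step 2: share of the attainable range.** This is 0.4b/(b − 17): 16/23 = 69.6% at 40, 18.4/29 = 63.4% at 46, 24/43 = 55.8% at 60 and 32/63 = 50.8% at 80. In points lost the order reverses: 16 at baseline 40, 32 at baseline 80.

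**Step 3: how many patients (assumed inputs).** The documents give neither a baseline distribution nor an expected mean change. Assume a normal baseline truncated at 40, with eight location and SD pairs from (44, 12) to (60, 12) giving means of about 50 to 61. Assume a mean change of −15, −20 or −25, independent of baseline, with SD 12.43 and scores clipped to 17–113.

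- Discordant patients: 0.2% to 2.9% of all. With follow-up totals rounded to whole points the upper end is 2.7%.
- Out of 470: 0.002 × 470 = 0.9 to 0.029 × 470 = 13.6, so about 1 to 14 patients over three arms.
- If change correlates −0.4 with baseline, the upper figure is 3.2%.
- A second set of assumptions (baseline mean 50 to 60, SD 7 to 10, mean change −18 to −26, SD of change 11.1 or 12.43, correlation −0.4) gives 0.1% to 2.3%.
- If one arm does better by the planned 4 units, the discordant share differs between arms by at most 0.6 percentage points.

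**Step 4: what the alternative would do.** Take response as (b − y)/(b − 17) ≥ 40%, that is y ≤ 17 + 0.6(b − 17). The cut-off is 17 + 0.6 × 23 = 30.8 at baseline 40 and rises with b, so every eligible remitter is a responder. But under the step 3 settings it adds 17 to 21 percentage points of responders.

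For a 4-unit effect, the difference in response rate between arms is 7 to 12 points, against 10 to 12 for the raw rule. One example (location 44, SD 12, mean about 51, change −20, 188 per arm):

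- Raw: 48.9% against 61.2%; z = 0.123/√[(0.489 × 0.511 + 0.612 × 0.388)/188] = 2.4.
- Floor-adjusted: 69.2% against 79.2%; z = 0.100/√[(0.692 × 0.308 + 0.792 × 0.208)/188] = 2.2.

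Over all settings z is about 2.2 to 2.4 for the raw rule and 2.0 to 2.4 for the adjusted one. The adjusted rule is slightly ahead only where the mean change is −15, or where the baseline is high and the mean change is −15; elsewhere it is level or behind.

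**The case for a change.** The best case for acting is that the mismatch comes from the documents' own numbers and needs no assumption. SAP 16.2 lists the variable among the efficacy variables, and SAP 10.0 promises by-visit LOCF results for all efficacy parameters, so it is likely to be reported. Adding a floor-adjusted version costs one definition line, removes every discordant pair and can leave the raw version in place. Failing that, one sentence and a remitter-by-responder count per arm would explain the odd rows.

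The arithmetic stands in full. The step from there to a fault in the plan does not:

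- A relative and an absolute threshold may cross without either being wrong. The ranking of remission above response comes from the reader; the visible text does not state it.
- Whether the raw rule is stricter for milder patients depends on the yardstick. It is stricter as a share of attainable range and more lenient in points (step 2).
- Missing explanation cannot be held against the plan. The protocol contents list a redacted section 9.7.5.3 directly after the secondary parameter, the SAP abbreviates a generalized linear mixed model that no visible section uses, and table specifications are in a separate document (SAP 4.0).
- The second variable would reclassify about a fifth of all patients to deal with at most about 3%. Its 40% threshold on the new scale has no basis in the documents. The raw variable would keep its discordant cases, and readers would face two response rates some 20 points apart.
- The sentence and the cross-tabulation are harmless, but they alter no estimate, test or conclusion.

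**Conclusion.** No change is needed. The crossing at baselines 40 to 46 is real and exact. It is a property of using one relative and one absolute cut-off near the entry threshold, and an analyst can code both variables without ambiguity. The rules are identical in all arms, so the comparison of response rates stays valid. The primary MMRM, the CGI-S analysis with its fixed sequence, and the sample size do not depend on them.

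The likely size is about 0.2% to 2.9% of patients, with a difference between arms of at most 0.6 percentage points. These shares rest on assumed baselines and mean changes; a trial population packed closely above the entry score of 40 could exceed them. Even then, the effect would be on how a descriptive category reads. The floor-adjusted variable swaps a small oddity for a large shift in the response rate and offers no dependable gain in separating the arms. A count of remitters coded as non-responders by arm is an option for the report and needs no amendment.

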16.3 AGE-AND-GENDER-CORRELATED VALUES FOR WEIGHT AND HEIGHT

To adjust weight (kg) and height (cm) for sex and age, one needs to compare them to standard reference values for the same sex and age group, which are available in the United States Growth Charts and can be downloaded from:
http://www.cdc.gov/growthcharts/percentile_data_files.htm

The z-score is calculated as below

$$z = \frac{(X / M)^L - 1}{SL}, \text{ if } L \neq 0 \text{ and}$$

$$z = \frac{\ln(X / M)}{S}, \text{ if } L = 0,$$

where X is the physical measurement (e.g. weight and height) and L, M and S are the values from the appropriate table corresponding to the age in months (or length/stature) and sex (1 = male; 2 = female). X must be in metric measurements (kilograms or meters). This is called LMS method (Cole TJ, 1990), and parameters L, M, and S are the Box-Cox transformation power, median, and standard deviation, respectively, in the reference data, which again are provided in the reference data tables.

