#### **9.7.6 Safety Analyses**

The safety analysis will be performed for the double-blind treatment period and double-blind down-taper period separately using the Safety Population. The safety parameters will include AEs, clinical laboratory parameters, vital sign measurements, ECG parameters, C-SSRS evaluations, and the change from baseline in the age and gender-adjusted height (evaluation of growth). For each safety parameter, the last assessment made before the first dose of double-blind investigational product will be used as the baseline for all analyses of that safety parameter.

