11.0 SAFETY ANALYSES

The safety analysis will be performed for the double-blind treatment period and the down-taper period (only for safety parameters collected during the down-taper period), separately, using the Safety Population unless stated otherwise.

The safety parameters include adverse events (AEs), clinical laboratory parameters, vital signs, electrocardiographic (ECG) parameters, suicide risk assessment using the Columbia-Suicide Severity Rating Scale (C-SSRS), and the change from baseline in the age and gender adjusted height (evaluation of growth). For each safety parameter, the last nonmissing safety assessment before the first dose of double-blind investigational product will be used as baseline for all analyses of that safety parameter. Continuous variables will be summarized by number of patients and mean, SD, median, minimum, and maximum values. Categorical variables will be summarized by number and percentage of patients.

For patients who take the down-taper investigational product, the double-blind treatment period starts with the first dose of double-blind investigational product and ends with the last assessment date up to the first dose of the down-taper investigational product. The double-blind down-taper period starts one day after the end of the double-blind treatment period and ends with the last dose of the down-taper investigational product or the last visit, whichever is later.

For patients who do not take the double-blind down-taper investigational product, the double-blind treatment period starts with the first dose of double-blind investigational product and ends with the last dose of the double-blind investigational product or the last visit, whichever is later.

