11.3 VITAL SIGNS

[figure not shown]
Descriptive statistics for vital signs (sitting radial pulse rate, sitting systolic and diastolic blood pressure, body weight and height) and their changes from baseline values at each visit, at the end of double-blind treatment period, and at the end of double-blind down-taper period will be presented by treatment group. Only patients with available baseline and at least 1 postbaseline assessment will be included in the summary.

[figure not shown]
Vital sign values will be considered PCS if they meet both the observed-value criteria and the change-from-baseline criteria listed in [Table 11.3–1](#). The number and percentage of patients with PCS postbaseline values will be tabulated by treatment group separately for the double-blind treatment period and the double-blind down-taper period. The percentages will be calculated relative to the number of patients with available baseline and at least 1 postbaseline assessment. The numerator will be the total number of patients with available baseline values and at least 1 PCS postbaseline value. A supportive listing of patients with PCS postbaseline values will be provided, including the PID number, and baseline and all postbaseline (including non-PCS) values.

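### SAP 16.3 gives height in both centimetres and metres for the growth z-score and never says that the measurement and the reference median must share a unit

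*SAP*

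**What the plan says.** Age- and sex-adjusted height is a named safety parameter in both documents. Protocol Section 9.7.6 lists "the change from baseline in the age and gender-adjusted height (evaluation of growth"), and SAP Section 11.0 lists "the change from baseline in the age and gender adjusted height (evaluation of growth").

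The derivation is in SAP Section 16.3, which begins: "To adjust weight (kg) and height (cm) for sex and age". It then gives the LMS formula:

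- z = ((X/M)^L - 1)/(S·L) if L is not 0
- z = ln(X/M)/S if L = 0

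Here X is the patient's weight or height and M is the reference median. On the source of the parameters it says: "L, M and S are the values from the appropriate table corresponding to the age in months (or length/stature) and sex". The unit of M is not stated. The same paragraph adds the rule "X must be in metric measurements (kilograms or meters").

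**The concern.** Kilograms can apply only to weight, so the unit left for height in the rule after the formula is metres. The opening sentence of the same section has height in centimetres. Weight is in kilograms in both places and is not affected.

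The ratio X/M is free of units only if X and M are in the same one. The section does not say so, and calling the measurement metric does not help, because centimetres and metres are both metric. The second statement is also worded as a requirement, so a programmer who follows it literally converts height to metres whatever the reference table contains.

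At stake is the evaluation of growth in a pediatric safety data set. Section 16.3 is the only derivation of that parameter in the available text.

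**Working it through.** The plan states no z-score to reproduce, so the check evaluates the SAP's own formula with matched and with mixed units.

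**Inputs.** The formula and the two height units come from SAP 16.3. L, M and S are not in the documents. Assumed: L from -1 to 2 and S from 0.04 to 0.05. For the worked examples, M = 140 cm and S = 0.045.

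**1. Matched units.** For a height 2% above the median, X/M = 1.02 whether both are in centimetres or both in metres. At L = 1, z = 0.02/0.045 = 0.444 either way. The choice of unit is irrelevant as long as it is shared.

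**2. X in metres, M in centimetres.** A child of median height has X/M = 0.01. The correct z is 0. The formula gives:

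| L | Expression | S = 0.05 | S = 0.04 |
|---|---|---|---|
| 2 | -0.9999/(2S) | -10.0 | -12.5 |
| 1 | -0.99/S | -19.8 | -24.75 |
| 0 | -4.605/S | -92.1 | -115.1 |
| -1 | -99/S | -1980 | -2475 |

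**3. X in centimetres, M in metres.** Now X/M = 100. The mildest case is L = -1, where z = 0.99/S = +19.8 to +24.75. At L = 0, z = +92.1 to +115.1. At L = 1, z = 99/S = +1980 to +2475.

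**4. Change from baseline, which is the parameter the plan names.** With X in metres and M in centimetres, and with L, M and S the same at both visits, write r for the correct ratio at each visit. The mixed-unit change is

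((0.01·r2)^L - (0.01·r1)^L)/(S·L) = 0.01^L × (correct change).

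The change is therefore multiplied by 0.0001 at L = 2, by 0.01 at L = 1, by 1 at L = 0 and by 100 at L = -1. For growth of 1 cm from 140 cm at S = 0.045:

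| L | Correct change in z | Mixed units |
|---|---|---|
| 1 | (1/140)/0.045 = 0.1587 | 0.0016 |
| 0 | ln(141/140)/0.045 = 0.1582 | 0.1582 |
| -1 | (1 - 140/141)/0.045 = 0.1576 | 15.76 |

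Holding L, M and S fixed is a simplification, because the table is entered by age in months. If L or S moves between visits, the error in the level no longer cancels from the change, even at L = 0.

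**The case against.** The bracketed units could be read as a loose pointer to the metric system rather than an order to use whole metres. On that reading centimetres qualify, the opening sentence sets the working unit, and there is no conflict. A programmer must also open the named reference table to compute anything and would see its unit there. This makes a correct analysis likely, but it does not remove the word meters from a sentence that says must.

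The sizes depend on assumed L and S, and the most extreme figures come from the ends of the assumed range of L. That stands. The only magnitude fixed by the documents is the factor of 100 in X/M. The named parameter is the change from baseline, not the level, and the effect on the change runs from none (L = 0, parameters fixed) to 100-fold in either direction for L between -1 and 1, and more beyond that. The size and direction of the error in the reported change are therefore not known from the documents.

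Parts of the protocol's safety analysis section are blacked out and table specifications are in a separate document, so another description of the method may exist out of view. That is why the claim is limited to the available text.

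Finally, z levels of -10 or worse would probably be caught on review, and SAP Section 11.3 reports "body weight and height) and their changes from baseline values at each visit" directly. Both points limit the damage. A table showing only changes would be less revealing, however: at L = 1 an error of this kind looks like almost no change.

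**Conclusion.** The section is wrong as written. It gives two units for one input, and whichever unit the reference median has, following one of them puts X/M out by a factor of 100. That conclusion needs no assumption about L, M or S.

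Under the assumed ranges (L from -1 to 2, S from 0.04 to 0.05), a median-height child would be placed at about -10 or lower if height is in metres against a median in centimetres, and at +19.8 or higher in the reverse case.

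The point is minor. It concerns one descriptive safety summary of height. Weight, the primary and secondary efficacy analyses, type I error control, power and sample size are not affected.

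**What to change.** In SAP Section 16.3, replace the sentence on metric measurements with: *X must be in the same unit as M in the reference table (weight in kg; height in the table's unit, to be confirmed as cm).*

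The requirement follows from the formula. The centimetre unit agrees with the section's opening sentence but should be checked against the table, because the documents do not give the unit of M.

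The cost is one sentence and there is no statistical downside. The SAP is marked final (05 Oct 2018), so the change would be made by amendment or recorded in a note to the programming specifications.
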